1.0 Objective

There is an urgent need for new non-invasive methods of focal deep brain stimulation. Existing methods of non-invasive transcranial neurostimulation include transcranial magnetic stimulation (TMS), direct current stimulation (tDCS), alternating current stimulation (tACS), and focused ultrasound (tFUS). All are limited in that they cannot stimulate deeper brain regions, at least

without confounding stimulation of the overlying cortex. This leaves unresolved debates about the causal roles of various deep brain structures in cognition, in particular the dorsal anterior cingulate cortex. Most of what is known about deeper regions in humans comes from fMRI studies, which show *correlation* but not *causation* between activity and cognition.

Likewise, a non-invasive deep brain stimulation method could open up new ways to treat a variety of clinical issues. Invasive stimulation of the nucleus accumbens has caused a dramatic loss of addiction in opioid users and those with alcohol dependence. Likewise cingulotomy has been used to treat OCD successfully, and Parkinson's disease can be treated with invasive stimulation of the subthalamic nucleus. The surgery required presents a barrier in all of these cases, making treatment impractical short of dire illness.

Temporal interference (TI) electrical neurostimulation is a new method of non-invasive deep brain stimulation. It works by applying several pairs of electrodes to the skull, each carrying different frequencies of alternating current. The individual currents are typically 2KHz or greater and thus are low-pass filtered by neuronal membranes so that they don't activate neurons. However where two different current frequency fields intersect, they create an interference pattern that oscillates at a beat frequency equal to the *difference* between the two applied frequencies. This beat frequency can be low enough to activate neurons, and the overlap field can be steered deep into the brain. Still, *it is relatively unknown whether TI can increase BOLD activity in deep brain regions, nor how TI may influence deeper brain regions involved in cognitive control, decision-making, and associated clinical conditions including addiction, schizophrenia, OCD, Parkinson's disease, and others.*

The overall objective of the present application is to develop and test Temporal Interference electrical neurostimulation by validating and characterizing its effects on human BOLD signals, and by demonstrating its usefulness in resolving longstanding debates about the function of a deeper brain region, the dorsal anterior cingulate cortex.

Aim 1: Test and characterize the effects of TI on the fMRI BOLD signal. We will apply TI to human subjects with fMRI. In **Study 1.1**, we will test the ability to focally activate the nucleus accumbens without activating the overlying cortex, and also its effects on functional connectivity. In **Study 1.2**, we vary the beat frequency parameter of TI to characterize its effects on BOLD inhibition vs. activation. In **Study 1.3**, we test the ability to stimulate a different deeper brain region, the dorsal ACC, and explore the optimal beat frequency.

Aim 2: Identify causal effects of dorsal anterior cingulate cortex (dACC) on cognition. We will apply TI to the dorsal ACC of human subjects with fMRI. In **Study 2.1**, we examine whether TI can disrupt or enhance the effect of conflict-monitoring signals on subsequent behavior. In **Study 2.2**, we test the theory that dACC drives motivation to avoid risk or loss, with subjects performing a previously published difficult forced-choice task while given the option to avoid the risk by skipping more difficult trials. We will test whether TI to dACC can change the probability of choosing to avoid risky choices. As time and resources permit, **Extra Study 2.3** will run a foraging task to ascertain whether TI to dACC will influence the choice probability to forage vs. influence RT when choices are most difficult.

Based on our own pilot data and others previous findings, we *hypothesize* that TI with a 20Hz beat frequency will cause increased fMRI BOLD activation in the targeted regions, without increasing activity in the overlying cortex. Further, we predict that a lower, 5Hz beat frequency may lead to BOLD inhibition as found previously. Moreover in Aim 2, we expect that TI will disrupt cognitive control signals in dACC, disrupt motivation to avoid risk or loss, and disrupt the probability of choosing to forage. If so, these findings will lay the foundation for testing clinical interventions with TI to disrupt addiction, OCD, and schizophrenia symptoms, which are known to

involve the dACC, as well as further applications of TI outside of dACC, such as non-invasive stimulation of the STN for Parkinson's disease, and the nucleus accumbens for addiction.

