In a set of pilot subjects (Modak et al., 2024), we applied 2mA per each channel of TI stimulation using the Soterix Interferential Neuromodulation System (Soterix Medical, Inc.), via carbon fiber electrodes while subjects were scanned with whole-brain fMRI (Fig. 2). Frequencies were 2000 Hz and 2020 Hz, for a 20Hz beat frequency. We aimed to target the left nucleus accumbens, and our finite element simulations predicted an optimal electrode placement with one channel at {F9, F10} in the EEG 10-10 locations and the other channel at {Fp1, CPz} (Fig. 2 top). Each subject received alternating 2 minutes on / 2 minutes off stimulation, with 30-second current ramp up and down. Sham stimulation consisted of current ramp up followed immediately by current ramp down, to control for initial scalp tingling(Gandiga et al., 2006). The sham stimulation will be controlled by the experiment script on a computer and is designed so that subjects will not be able to discern the difference between active and sham stimulation; the subject's experience will be the same, involving mild tingling in some subjects. Subjects received four sets of on/off stimulation for each of stimulation and sham conditions, with the order of on vs. off first counterbalanced. The results (Fig. 2 bottom) show increased BOLD signal in the region predicted by the finite element simulation. Moreover, when we changed the frequencies to be the same (i.e. 2000 Hz in both channels, the high frequencies remained, but the TI beat frequency was abolished. In 8 pilot subjects, the BOLD activation seen in Fig. 2 (bottom) was likewise abolished, which suggests that TI and not the high frequencies *per se* are essential for the BOLD activation observed. Our pilot subjects tolerated the stimulation well and revealed no substantial safety concerns. These pilot results will be tested more fully in **Aim 1**.

[figure not shown]

Fig. 2. Top: Finite element simulation prediction of TI effect of 2000Hz vs. 2020Hz at {F9, F10} and {Fp1, CPz}. Bottom: Increased fMRI BOLD effect due to TI in our pilot subjects (TI stimulation minus sham, Z statistic across n=16 subjects).

Characterizing the effect of TI on fMRI BOLD and cognition

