Power Analysis: From the pilot data shown in Fig. 2, we used the effect size of the stim-sham contrast to calculate the number of subjects required to detect a significant cluster of activity in the region shown. We assumed $p<0.001$ as the cluster defining threshold and required 90% power. The required number of subjects is 25, and we budget for 30 subjects per study to allow for attrition. We do not have effect size estimates for the behavioral effects of Aim 2.

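### Study 1.1 is to test target activation without overlying cortical activation, but the plan gives no cortical region, target-versus-cortex contrast or bound that could support the second half

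*Combined protocol and SAP*

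**What the plan says.** Section 1.0 states the hypothesis in two parts: 20 Hz TI "will cause increased fMRI BOLD activation in the targeted regions, without increasing activity in the overlying cortex". Under Aim 1 it makes both parts a task of Study 1.1: "we will test the ability to focally activate the nucleus accumbens without activating the overlying cortex".

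Section 3.0 describes the stimulation blocks of Study 1.1 (active, sham, and the same pair with both channels at 2000 Hz) and repeats the layout for Study 1.3 in the dorsal ACC. It gives no analysis of overlying cortex. Section 5.0, in the text available, covers Studies 2.1 to 2.3 only.

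The one numerical BOLD criterion is in the power paragraph of section 6.0. The sponsor writes that "we used the effect size of the stim-sham contrast" to find the number of subjects "required to detect a significant cluster of activity in the region shown", with p<0.001 "as the cluster defining threshold and required 90% power". The result: "The required number of subjects is 25, and we budget for 30 subjects per study to allow for attrition". The pilot map in section 2.0 is described as "TI stimulation minus sham, Z statistic across n=16 subjects"; the effect size is not given as a number.

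**The concern.** The hypothesis joins a positive claim (the target increases) to a negative one (the overlying cortex does not). The study is sized for the first. The second needs either a bound on the cortical effect or a direct comparison of target and cortex, and the plan has neither.

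With no stated rule, the easy course is to show a significant target beside a cortex with nothing above threshold and call the result focal. That does not test the difference between the two regions, and a non-significant cortex is not an unaffected one. The pilot account in section 2.0 already reasons this way: activation not seen in 8 subjects under equal frequencies is described as abolished.

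Much depends on it. Sections 1.0 and 2.0 fault existing methods for stimulating overlying cortex, and section 2.0 says this leads to confounds. Attributing the behavioural effects of Aim 2 to the dorsal ACC requires that cortical effects be bounded, not merely below threshold.

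**Working it through.** **Inputs.** From section 6.0: 25 subjects required, 30 budgeted, 90% power, cluster-defining p<0.001. From section 3.0: active and sham in the same subject, so the group test is one-sample on within-subject differences. Not stated: effect size, SD, sidedness for BOLD maps, smoothness, cluster-extent rule.

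**Step 1. The plan's own figure.** Without an effect size, 25 cannot be reproduced forward. It can be solved backward if the calculation is treated as a t-test at one location, which is an assumption. Power is P(T > t_crit), with T noncentral t on n-1 degrees of freedom and noncentrality d√n.

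- One-sided: t_crit(24 df) = 3.467. Power 0.90 needs noncentrality 4.864, so d = 4.864/5 = 0.97.
- Two-sided: t_crit = 3.745. Power 0.90 needs noncentrality 5.164, so d = 5.164/5 = 1.03.
- Normal approximation: (3.090 + 1.282)/5 = 0.87 and (3.291 + 1.282)/5 = 0.91.

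On this reading the study is sized for a large target effect.

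**Step 2. Smaller effects in cortex, same threshold, per location.** At n=30, t_crit(29 df) is 3.396 one-sided and 3.659 two-sided.

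| Cortical effect | d (one-/two-sided) | Power, n=25 | Power, n=30 |
|---|---|---|---|
| Half of target | 0.49 / 0.52 | 0.186 / 0.161 | 0.261 / 0.236 |
| Three-quarters of target | 0.73 / 0.77 | 0.578 / 0.559 | 0.718 / 0.711 |

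The half-size effect is missed 74-84% of the time and the three-quarter-size effect 28-44%. A fixed d=0.5, not tied to the back-solved value, has 14-20% power at n=25 and 21-28% at n=30.

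**Step 3. Does spatial extent change this?** Yes. Smooth group maps were simulated under assumed settings: 3 mm voxels, 8 mm FWHM smoothness, about 62,000 voxels, cluster-defining p<0.001, 5% familywise cluster extent, 150 runs per sample size. Detection of a uniform d=0.5 focus, over n=25 and 30 and both sidedness choices:

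| Focus radius | Detected |
|---|---|
| 6 mm | 6-12% |
| 10 mm | 49-73% |
| 15 mm | 87-98% |
| 20 mm | 99-100% |

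The values for broad foci are optimistic, because the effect is uniform and the noise correlation short-range. If subjects vary region-wide, power falls back toward Step 2. In the same simulation at n=25, a 6 mm focus is detected 81-87% of the time at d=0.9 and 94-95% at d=1.0. The back-solved d is therefore in line with a cluster calculation for a small target.

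**Step 4. Can the planned sample support a proper analysis?** Take a true cortical effect of zero.

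- A one-sided 95% upper limit falls below a bound of 0.5 SD with probability 78% at n=25 and 85% at n=30. For a bound of 0.3 SD the figures are 43% and 48%.
- The target-minus-cortex contrast has standardised effect d/√(2(1-r)), assuming equal SDs and correlation r. At r=0 this is 0.97/1.414 = 0.69, with 91% power at n=25 (two-sided 0.05); power is higher for larger d or r.
- If cortex truly responds at half the target, the contrast effect halves. Power at n=25 is then 38-42% at r=0 and 65-70% at r=0.5.

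**The case against.** The strongest reply is that the plan never says how focality will be judged. The p<0.001 value is a cluster-defining threshold inside a power calculation, not a decision rule, and no cluster-level alpha is given. That stands. A reader might infer that focality will be declared from the absence of a cortical cluster at p<0.001; the documents do not say so. But the alternative is that there is no criterion at all, and that needs the same remedy.

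Second, the percentages are for a single location and a back-solved effect, whereas clusters are detected by extent. That also stands. A reader might infer that the threshold misses most moderate cortical effects. Step 3 does not support this in general: the answer runs from mostly missed for a small focus to nearly always detected for a broad uniform one, and even per location a three-quarter-size effect is found more often than not.

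Third, section 6.0 is not the plan's only inference. Section 5.0 specifies an ANOVA, a logistic regression and BOLD contrasts for Aim 2, and section 3.0 specifies beat-frequency comparisons. None of these addresses overlying cortex. Nor is focality the lead test of Study 1.1: section 3.0 titles that study around control for the high-frequency carrier, and section 2.0 places the question of targeting specificity under Study 1.3. It remains a stated hypothesis and a stated test.

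Finally, a generous bound could license too much. An upper limit below half the target effect is compatible with real cortical activation. This is a fair limit on the remedy, so the reported wording has to follow the bound.

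**Conclusion.** The gap is real: a stated hypothesis and stated test of Study 1.1 has no analysis that could support it. This conclusion needs no arithmetic; it follows from the absence of a cortical region, contrast or bound in the available text.

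The size is conditional. If the sizing was in effect a single-location paired t-test, a half-size cortical effect has 16-19% power per location at n=25 and 24-26% at n=30. Detection of a whole cluster depends on its extent, which is unknown.

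The documents do not show that 25 subjects is wrong, since the pilot effect size is not given. Nor do they show that a sizeable cortical effect would go unreported; it could, chiefly if the focus is small. The trial can run as designed, but its focality conclusion should not be drawn without the analysis below.

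**What to change.** Before the images are analysed, add the following to the plan for Studies 1.1 and 1.3:

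1. Define a target mask and overlying-cortex masks from the finite element model. Split the cortical mask into local regions, for example under each electrode, so that averaging does not dilute a local effect. The simulation described in section 2.0 is for the left nucleus accumbens; Study 1.3 needs the same for its own montage.
2. Test focality as the within-subject contrast (stim minus sham in target) minus (stim minus sham in cortex), and report the cortical effect in each region with its confidence interval. Require the result in every cortical region before making an overall statement.
3. Tie the wording to the result. If the contrast is positive, conclude only that the effect is *stronger in the target than in overlying cortex*. If the upper confidence limit lies below a bound set in advance, report that *any cortical increase is smaller than [bound]*. Do not claim that cortex was not increased on the strength of a non-significant cortical map.
4. State the bound with its reason and its power. Step 4 shows that 0.5 SD is workable with 25 to 30 subjects and 0.3 SD is not. Those figures are for one region; requiring several regions to pass lowers them.

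The cost is SAP text and one region-level analysis of images already planned, with no extra subjects or scans. The sponsor may have to accept a weaker focality statement.

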2.0 Background

Need for new non-invasive deep brain stimulation. There is an urgent need for deep, focal, non-invasive, and cost-effective neurostimulation methods in humans. Both basic science and clinical needs are pressing. Much of the basic cognitive neuroscience research in humans focuses on fMRI or EEG, which can show neural *correlates* of behavior but cannot show neural *causes* of behavior, strictly speaking. Likewise clinically, many targets for intervention in addiction (nucleus accumbens) and OCD (anterior cingulate) lie deep in the brain, beyond the reach of common transcranial electrical neurostimulation methods like tDCS, tACS and standard TMS. Some deep TMS methods are now FDA-approved to target deep structures like the ACC, but these lack focality and stimulate a range of areas across the prefrontal cortex(Harmerlech et al., 2021). Transcranial focused ultrasound (tFUS) can provide focal stimulation (sonication) of deep structures but requires invasive skull fixation(Webb et al., 2022). A cost-effective method that allows deep, focal, non-invasive neurostimulation in humans, without also stimulating the overlying superficial cortical regions, would allow answers to many basic questions about the causal role of particular deep brain regions in cognition, especially cognitive control. Moreover, it may open the door to a number of potential clinical treatments, especially if the equipment can be made inexpensive and portable.

Temporal interference (TI) electrical neurostimulation has the potential to provide such a non-invasive deep brain stimulation method(Grossman et al., 2017). TI(C. C. Brown, 1975; Pope et al., 1995) works by administering two or more alternating currents of slightly different frequencies (Figure 1). These frequencies are typically too high to cause significant neural stimulation, on the order of 2KHz or higher, as they are filtered out by a neurons cell membrane, which acts as an electrical low-pass filter. Where two fields of slightly different frequencies overlap, they create an interference pattern (the beat frequency), with a frequency equal to the difference of the two carrier frequencies. This is analogous to the beat frequency created by plucking two guitar strings that are slightly out of tune with each other. This interference pattern can be aimed at deep brain regions, where the lower interference pattern frequency can cause neural stimulation without stimulating the more superficial cortical regions(Grossman et al., 2017). Such an effect requires at least four electrodes, with two pairs of alternating current electrodes. Early results in rodents showed that TI could be administered effectively and without tissue damage(Grossman et al., 2017). Subsequent studies also showed that high-frequency TI affects the sharp-wave ripples in hippocampus and suppresses epileptic biomarkers in mouse models(Acerbo et al., 2022) and may influence neural activity(Wessel et al., 2023) and memory encoding in humans(Acerbo et al., 2022; J. W. Brown, 2023; Violante et al., 2023). Theoretical results suggest how TI may activate sodium channels, essentially “jiggling” them open, but without activating hyperpolarizing currents in individual neurons(Cao et al., 2020).

[figure not shown]

Fig. 1. Temporal interference electrical neurostimulation.
Stimulation occurs where the electric fields intersect, but not from either field individually¹². This allows deep regions

The potential implications are profound – the method may allow a number of basic science questions about the causal role of deeper brain structures to be answered, and moreover, it may allow new treatments for a number of clinical disorders that involve dysfunction of deeper brain structures (e.g. addiction(Müller et al., 2009; Zhou et al., 2011), OCD(Kim et al., 2003), and pain(Corkin et al., 1979) among others).

Developing TI neurostimulation for use in humans. Previous work by us and others has shown that TI can be safely used in humans with fMRI and may have modest value as an intervention on behavior (Modak et al., 2024; Violante et al., 2023; Wessel et al., 2023). It remains unclear exactly how TI may influence neural activity and cognitive function in healthy humans as measured by fMRI BOLD responses, and specifically how variations in the TI beat frequency may contribute to the effectiveness of TI stimulation (Aim 1), as well as how TI may influence cognitive processes in deeper brain regions (Aim 2). The present work will address these directly, showing the nature of the effects on both BOLD signals and cognition, the safety of the effects, and will provide a foundation for future work both to understand the causal role of deep brain regions in cognitive functions and develop new clinical treatments. We will first test the effects of TI on human brain activity and then demonstrate the utility of TI to adjudicate long-standing questions about the causal role of deeper brain structures in cognition, especially the dorsal anterior cingulate cortex.

Preliminary results of combined TI and fMRI

In a set of pilot subjects (Modak et al., 2024), we applied 2mA per each channel of TI stimulation using the Soterix Interferential Neuromodulation System (Soterix Medical, Inc.), via carbon fiber electrodes while subjects were scanned with whole-brain fMRI (Fig. 2). Frequencies were 2000 Hz and 2020 Hz, for a 20Hz beat frequency. We aimed to target the left nucleus accumbens, and our finite element simulations predicted an optimal electrode placement with one channel at {F9, F10} in the EEG 10-10 locations and the other channel at {Fp1, CPz} (Fig. 2 top). Each subject received alternating 2 minutes on / 2 minutes off stimulation, with 30-second current ramp up and down. Sham stimulation consisted of current ramp up followed immediately by current ramp down, to control for initial scalp tingling(Gandiga et al., 2006). The sham stimulation will be controlled by the experiment script on a computer and is designed so that subjects will not be able to discern the difference between active and sham stimulation; the subject's experience will be the same, involving mild tingling in some subjects. Subjects received four sets of on/off stimulation for each of stimulation and sham conditions, with the order of on vs. off first counterbalanced. The results (Fig. 2 bottom) show increased BOLD signal in the region predicted by the finite element simulation. Moreover, when we changed the frequencies to be the same (i.e. 2000 Hz in both channels, the high frequencies remained, but the TI beat frequency was abolished. In 8 pilot subjects, the BOLD activation seen in Fig. 2 (bottom) was likewise abolished, which suggests that TI and not the high frequencies *per se* are essential for the BOLD activation observed. Our pilot subjects tolerated the stimulation well and revealed no substantial safety concerns. These pilot results will be tested more fully in **Aim 1**.

[figure not shown]

Fig. 2. Top: Finite element simulation prediction of TI effect of 2000Hz vs. 2020Hz at {F9, F10} and {Fp1, CPz}. Bottom: Increased fMRI BOLD effect due to TI in our pilot subjects (TI stimulation minus sham, Z statistic across n=16 subjects).

Characterizing the effect of TI on fMRI BOLD and cognition

The most fundamental open question here is how TI may influence activity as measured by the fMRI BOLD signal. New work suggests TI at 5 Hz beat frequency may suppress BOLD activity (Violante et al., 2023), but our pilot data with a 20 Hz beat frequency suggests TI may increase BOLD activity. **Study 1.1** will test whether a 20Hz beat frequency TI may increase BOLD activity. Second, it remains to be established whether the BOLD effects are due to the beat frequency rather than an overlap of two high frequency signals of the same frequency. **Study 1.1** also includes a comparison between 20Hz beat frequency TI vs. a control condition of zero Hz beat frequency, i.e. when the two electrode pairs have the same frequency (2000Hz). Third, because theoretical work suggests that higher beat frequencies may cause more neural excitation(Cao et al., 2020), we will directly compare 5 Hz TI vs. 20 Hz TI in **Study 1.2**. Fourth, it remains to be established how specifically TI can target various deep brain regions. In preparation for Aim 2, we will test how well TI at 20 Hz can focally target the dorsal anterior cingulate cortex (around MNI 0, 30, 30) (**Study 1.3**).

Resolving long-standing debates about the role of dorsal anterior cingulate cortex

The causal role of several deep brain regions in cognition remains unresolved. This is because we have lacked a method to temporarily and non-invasively disrupt deep brain regions without also disrupting the overlying cortex, which leads to confounds. This limitation applies to transcranial direct and alternating current stimulation, and transcranial magnetic stimulation, even with deep TMS coils(Harmerlech et al., 2021). Transcranial focused ultrasound holds some promise(Kubanek, 2018) but can only minimize the superficial stimulation, not eliminate it.

The function of the dorsal anterior cingulate cortex (dACC) in particular, including the adjacent medial prefrontal cortex, remains contested and has been the focus of vigorous and unresolved debate for nearly three decades(Clairis & Lopez-Persem, 2023). Almost all functional arguments are based on measurements of activity rather than manipulations, and so the evidence shows functional correlates rather than the causal roles. TI stimulation provides a fresh path forward to resolve some of these longstanding debates. An early theory proposed that dACC signaled conflict and thus increased control, as evidenced by the Gratton effect, in which response conflict leads to slower responses on subsequent trials(Botvinick et al., 1999). However neuropsychological studies have yielded mixed results(Fellows & Farah, 2005; Sheth et al., 2012). We will test this in **Study 2.1**. Other findings suggest a different function, i.e. that dACC drives motivation(Parvizi et al., 2013), especially to avoid risk or loss(J. W. Brown & Braver, 2007; Magno et al., 2006), which we will test in **Study 2.2**. Still others have argued that dACC drives foraging behavior(Kolling et al., 2012), with ongoing debate on whether apparent foraging value represents difficulty instead(Kolling et al., 2016; Shenhav et al., 2014), or perhaps prediction errors in service of learning(J. W. Brown & Alexander, 2017). We may test this in **Extra Study 2.3**. The unresolved debates in turn hinder our ability to understand dysfunctions of the dACC and its roles in clinical disorders such as addiction(Fishbein et al., 2005; Forster et al., 2016), OCD(Fitzgerald et al., 2005), and schizophrenia(Adams & David, 2007). In Aim 2, we apply TI to test for causal roles of dACC on behavior, with the goal of adjudicating the ongoing debates.

